10.4 Analysis Approach

Analyses will employ modeling approaches that are less sensitive to biases from missing data, using a technique that conceptualizes missing data in two ways: intermittent missing data for participants active in the trial and dropouts (Shoptaw et al., 2002). Analysis of urine drug screen results are conducted using aggregates such as the Treatment Effectiveness Score (Ling et al., 1997), which is tested by condition using GLM and non-parametric strategies, where appropriate. Retention differences between conditions will be tested using an appropriate survival analysis model. Counts and composites of scores on drug craving and psychological measures will also be analyzed by treatment condition using t-tests and ANOVAs. Secondary analyses may include use of longitudinal models (Diggle et al., 1994), including normal mixed-effects models (Littell et al., 1996; SAS Institute, 1996; Singer, 1998; MIXED; PROC MIXED, SAS Institute Inc, Cary, NC) for continuous measures and generalized linear mixed models (Littell et al., 1996; GLMM; GLIMMIX macro, SAS Institute, Inc) for categorical measures. A six-step analysis approach is described below.

10.4.1 Data Screening

Typical data screening activities will be conducted; univariate analyses will determine cell frequencies, normality, linearity, and homoscedasticity of continuous variables, and missing values. Variables with non-normal distributions will be transformed, when appropriate, using procedures recommended by Mosteller and Tukey (1977). Missing values will be handled using conventional case elimination, mean substitution, or estimation procedures (e.g. Cohen & Cohen, 1983). Preliminary analyses will address baseline characteristics of the two medication conditions using univariate techniques to determine the adequacy of the random assignment procedures, and whether these procedures result in groups similar in pertinent characteristics. Any variables determined to differ significantly between conditions will be used as covariates. We will also conduct attrition analyses to determine whether participants who failed post-consent screening differ from those randomized.

Baseline Characteristics and Treatment Group Differences

To appraise differences in baseline characteristics of the treatment groups, continuous variables will utilize analysis of variance, ordinal variables will utilize the Cochran Mantel Haenszel test, and dichotomous variables will utilize the chi-square (χ^2) test or Barnard's test. As appropriate, transformation such as log, square root or inverse may be utilized to accomplish the twin goals of variance stabilization across levels of the predictor variables and normal distribution of the outcome variable, if necessary.

For continuous variables, the number of non-missing and missing values and the median, mean, standard deviation, minimum, and maximum will be obtained for each treatment group. For categorical variables, the counts and proportions of each value will be tabulated.

Differences between participants who were considered but not randomized (screen fails) will be compared with randomized participants on selected demographic characteristics. Summary tables for continuous variables include mean, standard deviation, median, min and max will be prepared. Outcome measures will be summarized by treatment group and by visit when applicable.

Treatment group differences at the 0.10 level of significance in baseline variables may be included as stratification variables or covariates in efficacy analyses.

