7.3 Random Assignment

Eligible participants will be randomly assigned to study condition (VI, PNV, DE) in a 1:1:1 strategy using an urn randomization procedure (Stout et al., 1994) to provide multivariate balance across two characteristics correlated with outcomes in addiction treatment trials: type of opioid (heroin or prescription drug) and gender.

Individuals who terminate participation before induction onto the assigned medication (or similar time-point for behavioral assignments) will be replaced. Those terminating after VI induction or provision of the first DE session will not be replaced and will be counted as "treatment failures" (in an intent-to-treat scenario).

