10.0 STATISTICAL ANALYSES

The project emphasizes evaluation of the clinical utility of Vivitrol in jail inmates as compared with a Drug Education condition (DE), while descriptive statistics will provide an overall assessment of the implementation of the protocol.

Analyses will include an Intent-to-treat (ITT) design such that all randomized participants who received at least one dose of medication (VI, PNV), or received at least one session of drug education (DE) will be included who did not violate the protocol in a way that could potentially affect the efficacy results. Participants will be excluded from the Protocol Population (PP) if:

- 1. concomitant medication that is known to have significant clinical effect on primary or secondary endpoints was administered.
- 2. Violations of the inclusion or exclusion criteria are judged to affect the efficacy evaluations.

Subjects in the PP population will be allocated to treatment groups in the analysis based on the actual treatment they received. If there is substantial difference between the ITT population and the PP population, all analyses described below will be performed using only subjects in this group.

All statistical tests will be performed using two-sided .05 significance levels, unless otherwise stated. All comparisons between treatments will be reported with parameter estimates and 95% confidence intervals. For parameters measured at baseline and subsequently, the variables of interest are changes from baseline.

Post-baseline variables will not be imputed; estimates can be obtained using the hierarchical models specified below under the assumption of missing at random. For the primary outcome measure, diagnosis at six months, subjects who have dropped out for whatever reason will be considered to retain the diagnosis. Other outcome measures for which data are missing will be imputed using multiple imputation methods. Sensitivity analyses will repeat specific analyses using permutation tests of at least 1000 samples.

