10.4.2 Primary Statistical Analysis of the First Primary Outcome Measure

A mixed effects logistic regression will used to model the binary primary outcome measure; the diagnosis of opioid use disorder at six months post treatment. are modeled as a linear combination of predictor variables. A logit link function will be used to link subject covariates to the probability of success There will be two levels in the model: within sites and between sites. The model will included treatment, cluster (site) and baseline covariates as fixed effects and subject as a random effect. Indicator variables will identify whether a subject has received XR-NTX, methadone and a behavioral intervention (PN.) Site by treatment interactions will be included in the model. Interactions that are statistically significant at the 10% level will be investigated and may imply that analyses of individual sites is required. In this case, relevant contrasts will be performed within the sites.

Additional covariates will include age, gender, whether a subject had prior methadone maintenance treatment and baseline self-reported cocaine use. Other possibilities mediating

factors include opioid dependence severity at baseline, concurrent cocaine or alcohol and/or benzodiazepine misuse, and homelessness.

SAS PROC Mixed will be used to perform the analysis. The coefficients in the model will be estimated by generalized least squares (GLS), with covariance parameters estimated by restricted maximum likelihood (REML). Standard errors of the parameter estimates will be computed using the model. This procedure assumes that missing observations are ignorably missing or missing at random (MAR).

The primary contrast is a comparison of the probability of a DSM-5 Opioid Use Disorder Diagnosis at 6 months for those on medication versus those receiving enhanced treatment as usual (etau.) The contrast will utilize XR NTX data from both the NYU and UCLA and Interim Methadone data from FRI; the medication plus PN treatment arm will not be included.

Descriptive statistics will examine feasibility issues of the pharmacotherapy, analyzing AEs, side effects, and patient and clinician acceptance, and reasons for early termination or post-randomization refusal of assigned condition. Single-point, between-group comparisons of these measures can be tested using t-tests or ANOVAs for continuous variables and chi-square for binary measures.

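### Covariates are added on baseline significance under two unreconciled rules, so the primary model is not fixed and may omit opioid type

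*Combined protocol and SAP*

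**What the plan says.** Section 10.4.1 contains two rules for choosing covariates from the data.

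- **Rule 1.** "Preliminary analyses will address baseline characteristics of the two medication conditions using univariate techniques", followed by "Any variables determined to differ significantly between conditions will be used as covariates". No significance level is given here. Section 10.0 supplies a default: "All statistical tests will be performed using two-sided .05 significance levels, unless otherwise stated".
- **Rule 2**, later in the same section: "Treatment group differences at the 0.10 level of significance in baseline variables may be included as stratification variables or covariates in efficacy analyses".

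Section 10.4.2 describes the primary model for the six-month diagnosis: "The model will included treatment, cluster (site) and baseline covariates as fixed effects and subject as a random effect". It then names four covariates: "Additional covariates will include age, gender, whether a subject had prior methadone maintenance treatment and baseline self-reported cocaine use". After these it mentions further possible "factors include opioid dependence severity at baseline, concurrent cocaine or alcohol and/or benzodiazepine misuse, and homelessness", with no rule for when they enter.

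Section 7.3 balances the urn randomisation on "type of opioid (heroin or prescription drug) and gender" and describes both as related to outcome in addiction trials. Gender is among the four covariates in section 10.4.2. Opioid type is not.

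**The concern.** A covariate earns its place in a randomised comparison by predicting the outcome. A baseline test asks a different question, namely whether the arms happen to differ, and under correct randomisation a significant answer is a chance finding. A strong predictor that is nearly balanced is left out, and an irrelevant variable that is imbalanced is brought in.

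Two further problems are specific to this plan. First, the tests are not aligned with the primary contrast. Section 10.4.2 compares medication with enhanced treatment as usual and leaves out the arm with patient navigation. Rule 1, as worded, compares the two medication conditions with each other. Rule 2 covers the treatment groups generally, so a difference driven only by the navigation arm could trigger it. Second, the rules leave choices open. One is mandatory and the other optional, and section 10.4.2 adds unnamed baseline covariates and a list of candidates without a decision. The trial is open-label (section 7.14), and the locked data go to the principal investigator for analysis (section 12.5). Several adjusted versions of the primary result would therefore be compatible with the plan, with arm assignment visible to whoever chooses.

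**Working it through.** The plan states no figure that depends on the covariate rules, so there is nothing to reproduce. The check compares the rules and then sizes how often they would act.

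**Comparison of the rules**

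| | Rule 1 | Rule 2 |
|---|---|---|
| Level | None written; .05 two-sided by inference from section 10.0 | 0.10, written |
| Force | Mandatory | Optional |
| Groups | The two medication conditions | Treatment groups |
| Use | Covariate | Covariate or stratification variable |

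Neither rule refers to the other, and section 10.4.2 does not switch either off.

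**Chance of a false flag**

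Inputs: levels .05 (section 10.0) and 0.10 (section 10.4.1). The number of baseline variables tested, k, is not stated, so a range of 5 to 20 is assumed. The tests are taken as independent and randomisation as correct.

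Chance of at least one flag = 1 − (1 − α)^k. If all four covariates named in section 10.4.2 are among those tested, flagging them changes nothing, so the exponent for new additions is k − 4.

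| k | Any flag, .05 | Any flag, .10 | New addition, .05 | New addition, .10 |
|---|---|---|---|---|
| 5 | 1 − .95^5 = 22.6% | 1 − .90^5 = 41.0% | 1 − .95^1 = 5.0% | 1 − .90^1 = 10.0% |
| 10 | 1 − .95^10 = 40.1% | 1 − .90^10 = 65.1% | 1 − .95^6 = 26.5% | 1 − .90^6 = 46.9% |
| 20 | 1 − .95^20 = 64.2% | 1 − .90^20 = 87.8% | 1 − .95^16 = 56.0% | 1 − .90^16 = 81.5% |

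The expected number of flags is kα; at k = 10 this is 0.5 at .05 and 1.0 at .10.

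If both levels were applied to the same comparison, they would select different sets whenever a p-value fell between .05 and .10. That has probability .05 per variable, so 1 − .95^k: 22.6%, 40.1% and 64.2% for k = 5, 10 and 20.

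**Effect on the test**

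An illustrative simulation used 6,000 runs, 50 against 50, a continuous outcome and ten independent baseline variables that jointly explain 30% of outcome variance. All these settings except the arm size are assumptions.

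| Adjustment | Type I error | Power at 0.5 SD |
|---|---|---|
| None | .047 | .69 |
| Selected at .05 | .038 | .70 |
| Selected at .10 | .038 | .70 |
| Fixed set of all ten | .051 | .81 |

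With a true effect of 0.5 SD, the two selection levels led to different significance conclusions in about 5% of runs. Selection gained almost nothing over no adjustment, whereas the fixed set gained about 11 percentage points of power.

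**The case against.** The strongest reply is that the plan already has a mandatory core of four covariates, that section 10.3 presents the study as preliminary, and that a flagged variable is not in itself a harm. Much of this stands. The core limits what the rules can change. The simulation does not include that core, and its outcome is continuous, whereas the primary outcome is binary. Its power gap indicates direction and is not an estimate for this trial.

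It can also be argued that imbalance here need not be chance. Only the medication arms face a naloxone challenge (section 2.4), and a repeated failure makes a participant ineligible (section 7.4.1). Those who leave before induction are replaced (section 7.3), the analysis set requires a dose or a session (section 10.0), and the primary contrast pools data from other sites. That stands too: the percentages above describe correct randomisation and not every feature of the analysed set. It does not make a significance test a good way to choose covariates.

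A reader might infer several stronger points that the documents do not support:

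- **The rules override a fixed list.** They only add to the four covariates, and that list is not closed.
- **The plan writes two thresholds.** Only 0.10 is written; .05 is inferred from a default that gives way where another level is stated. The certain conflict is between mandatory and optional inclusion.
- **Type I error is inflated.** Mechanical selection was slightly conservative in the simulation.
- **Extra covariates cost precision because each arm has only 40 to 50 participants.** Section 10.4.2 pools sites whose numbers are not given, and section 10.0 counts dropouts as keeping the diagnosis, so that is not the size of the primary model.

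**Conclusion.** The point holds. Section 10.4.1 has two unreconciled rules that select covariates on baseline significance, and section 10.4.2 leaves its own list open, so the primary model is not fixed in advance. Rule 1 as worded does not examine the primary contrast. Opioid type, which section 7.3 treats as prognostic, is unnamed in section 10.4.2. Because the urn balances it, it is also unlikely to be picked up by testing.

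The chance of at least one false flag is 23% to 64% at .05 and 41% to 88% at .10, assuming 5 to 20 independent variables and correct randomisation. It is lower for new additions to the model. These are chances that the rules act, not chances of a wrong conclusion. The harm is discretion over the model in an open-label trial and probably lost power against fixed prognostic adjustment, by an amount that the documents do not allow one to state. The plan should be changed, but the point does not by itself undermine the trial.

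**What to change.** 1. Delete both significance-based sentences from section 10.4.1.
2. In section 10.4.2, before outcomes are examined by arm, close the primary covariate list as age, gender, prior methadone maintenance, baseline cocaine use and opioid type. In an open-label trial, unblinding is not a usable time point for this.
3. Give an explicit yes or no for each further candidate in section 10.4.2. Baseline opioid use disorder severity is a reasonable one to consider, since section 8.2.4 collects it at screening. Opioid use before incarceration is less secure: the screening Timeline Follow-Back covers only the prior 30 days (section 8.2.1), which may have been spent in custody.
4. Report baseline balance descriptively, by arm and without tests.
5. Handle a notable imbalance in an unlisted variable in a sensitivity analysis labelled as such.

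The cost is wording only. Opioid type is already needed for the urn in this trial; whether the other pooled sites recorded it is not stated and should be confirmed before the list is closed. The small downside is that a chance imbalance in an unlisted variable would no longer alter the primary estimate.

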10.4.2 Primary Statistical Analysis of the First Primary Outcome Measure

A mixed effects logistic regression will used to model the binary primary outcome measure; the diagnosis of opioid use disorder at six months post treatment. are modeled as a linear combination of predictor variables. A logit link function will be used to link subject covariates to the probability of success There will be two levels in the model: within sites and between sites. The model will included treatment, cluster (site) and baseline covariates as fixed effects and subject as a random effect. Indicator variables will identify whether a subject has received XR-NTX, methadone and a behavioral intervention (PN.) Site by treatment interactions will be included in the model. Interactions that are statistically significant at the 10% level will be investigated and may imply that analyses of individual sites is required. In this case, relevant contrasts will be performed within the sites.

Additional covariates will include age, gender, whether a subject had prior methadone maintenance treatment and baseline self-reported cocaine use. Other possibilities mediating

factors include opioid dependence severity at baseline, concurrent cocaine or alcohol and/or benzodiazepine misuse, and homelessness.

SAS PROC Mixed will be used to perform the analysis. The coefficients in the model will be estimated by generalized least squares (GLS), with covariance parameters estimated by restricted maximum likelihood (REML). Standard errors of the parameter estimates will be computed using the model. This procedure assumes that missing observations are ignorably missing or missing at random (MAR).

The primary contrast is a comparison of the probability of a DSM-5 Opioid Use Disorder Diagnosis at 6 months for those on medication versus those receiving enhanced treatment as usual (etau.) The contrast will utilize XR NTX data from both the NYU and UCLA and Interim Methadone data from FRI; the medication plus PN treatment arm will not be included.

Descriptive statistics will examine feasibility issues of the pharmacotherapy, analyzing AEs, side effects, and patient and clinician acceptance, and reasons for early termination or post-randomization refusal of assigned condition. Single-point, between-group comparisons of these measures can be tested using t-tests or ANOVAs for continuous variables and chi-square for binary measures.

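### Section 10.4.2 specifies a logit model for the 6-month diagnosis but fits it with a linear procedure and a subject random effect that one diagnosis per person cannot support, so it does not fix which estimate and interval are reported

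*Combined protocol and SAP*

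**What the plan says.** Section 10.4.2 describes the primary analysis of the 6-month diagnosis in terms that belong to two different models.

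- Model: "A mixed effects logistic regression will used to model the binary primary outcome measure", and "A logit link function will be used to link subject covariates to the probability of success".
- Software and estimation: "SAS PROC Mixed will be used to perform the analysis", and then "The coefficients in the model will be estimated by generalized least squares (GLS), with covariance parameters estimated by restricted maximum likelihood (REML").
- Structure: "There will be two levels in the model: within sites and between sites". The model nevertheless has "cluster (site) and baseline covariates as fixed effects and subject as a random effect", and it includes site-by-treatment interactions.
- Target: "The primary contrast is a comparison of the probability of a DSM-5 Opioid Use Disorder Diagnosis at 6 months", medication against enhanced treatment as usual. "The contrast will utilize XR NTX data from both the NYU and UCLA and Interim Methadone data from FRI"; the arm with medication plus patient navigation is left out.

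Four other sections bear on this:

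- Section 8.2.4 schedules the diagnosis at screening and at 6 months.
- Section 5.3.1 makes the disorder an entry criterion.
- Section 10.4, for secondary analyses only, pairs PROC MIXED with continuous measures and the GLIMMIX macro with categorical ones.
- Section 10.0 promises a parameter estimate and a 95% confidence interval for every treatment comparison, but does not name the effect measure.

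**The concern.** PROC MIXED with GLS and REML is a normal-theory linear fit. Its treatment coefficient on a 0/1 outcome is a risk difference. A logit model gives a log odds ratio. An analyst cannot run PROC Mixed as named and also report the stated logit model.

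A random subject effect needs repeated informative observations within a person. Here everyone has the disorder at screening, so only the 6-month value varies. The two levels named are within and between sites, yet site is fixed, so nothing in the described structure calls for a subject effect.

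What is at stake is the estimate and its interval, more than the test. Section 10.3 says the trial is meant to give a preliminary characterisation of outcomes for a larger multi-site trial. The planners of that trial will use the effect size and its precision, and section 10.4.2 does not say which effect that will be.

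**Working it through.** The plan gives no diagnosis rates and no pooled sample size, so it has no figure of its own to reproduce. The example below uses 50 per arm (section 10.3) and assumed 6-month diagnoses in 35/50 drug education (DE) and 25/50 Vivitrol (VI) participants. Effects are DE relative to VI. It is one site without site terms, so it illustrates the problem and is not the pooled contrast.

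1. **Linear model, as PROC Mixed would fit it.**
   - Difference = 0.70 − 0.50 = 0.20.
   - Residual variance = (50×0.7×0.3 + 50×0.5×0.5)/98 = (10.5 + 12.5)/98 = 0.2347.
   - SE = √(0.2347×2/50) = 0.0969.
   - 95% CI 0.008 to 0.392, p = 0.042.
   - With one value per person, the subject and residual variances enter only as their sum. Assigning 0, 25, 50 or 90% of the 0.2347 to subject leaves the REML likelihood, the coefficient and the SE unchanged. The subject term is redundant, and the risk difference is unique.

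2. **Ordinary logistic regression, no subject effect.**
   - OR = (35/15)/(25/25) = 2.33.
   - SE of log OR = √(1/35 + 1/15 + 1/25 + 1/25) = 0.4186.
   - 95% CI = exp(0.8473 ± 1.96×0.4186) = 1.03 to 5.30, p = 0.043.
   - Log-likelihood = 35 ln 0.7 + 15 ln 0.3 + 50 ln 0.5 = −65.2006.

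3. **Logistic regression with a normal subject intercept of SD s.** For any s, the two coefficients can be chosen so that the averaged probabilities are exactly 0.70 and 0.50. The likelihood is therefore the same at every s (80-point quadrature):

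| Imposed subject SD | Subject-specific OR (95% CI) | p | Log-likelihood | Risk difference |
|---|---|---|---|---|
| 0 | 2.33 (1.03 to 5.30) | 0.043 | −65.2006 | 0.20 |
| 1 | 2.77 (1.04 to 7.39) | 0.042 | −65.2006 | 0.20 |
| 2 | 3.99 (1.05 to 15.1) | 0.042 | −65.2006 | 0.20 |
| 3 | 6.19 (1.07 to 35.7) | 0.042 | −65.2006 | 0.20 |

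   The SDs are imposed to show that the likelihood is flat. The plan sets none of them.

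4. **With covariates.** Take 200 simulated datasets, 50 per arm, with logit = −0.3 + 0.85×DE − 0.2×age (SD units) + 0.2×male + 0.6×cocaine − 0.2×prior methadone. The shares are 87% male (the jail's figure in section 5.5), 40% cocaine and 30% prior methadone. Everything except the male share is assumed.
   - Over SD 0 to 3 the log-likelihood varies by a median of 0.04 and at most 0.41. Telling the SDs apart at the usual 5% level needs 3.84/2 = 1.92.
   - The median OR at SD 0, 1, 2 and 3 is 2.53, 3.05, 4.59 and 7.43.
   - The standardised risk difference moves by a median of 0.002 and at most 0.017.
   - A second simulation with other assumed coefficients (57 fitted datasets) gave log-likelihood ranges of median 0.08 and maximum 0.64, which leads to the same conclusion.

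**The case against.** The strongest reply is that the procedure is merely misnamed. Linearised fitting of a generalised linear mixed model does use a logit link together with GLS and REML steps, and section 10.4 already names the GLIMMIX macro for categorical measures. On the example, such a fit with the residual dispersion held at 1 estimates a subject variance of 0.09 and OR 2.33 (1.02 to 5.35), almost ordinary logistic regression. A misnaming is quite possible. But section 10.4.2 does not name that method, and section 10.4 speaks of secondary analyses. Nor does it remove the identification problem: with the dispersion also free, the fit diverged.

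Second, PROC Mixed taken literally gives one risk difference with one interval, and the p-value hardly moves. Both points stand. A reader might infer from the table that the effect is wholly undetermined, or that the plan could report an odds ratio near 6. The documents do not support that. They fix no subject SD, the larger ratios come from SDs imposed here, and the linearised estimator at SD 1, 2 and 3 gives only 2.40, 2.72 and 3.17.

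Third, the contrast pools three projects, and the other two may record the diagnosis more often. That cannot be seen here; sections 8.2.4 and 5.3.1 describe this protocol only. The contrast is still a single 6-month comparison.

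A reader might also see a conflict between the missing-at-random sentence in section 10.4.2 and the handling of dropouts. Sections 10.0 and 7.3 largely settle this: dropouts are counted as still having the diagnosis, so once coded they are not missing. Any remaining wording question there is separate from this point.

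**Conclusion.** The point holds in a limited form. Section 10.4.2 names a logit model and a linear procedure for the same outcome, and adds a subject random effect that is redundant in the linear model and not identified in the logistic one (only weakly identified with covariates). It therefore does not settle which estimate and 95% CI, required by section 10.0, will be reported. In the assumed example the candidates are a risk difference of 0.20 (0.01 to 0.39), an ordinary OR of 2.33 (1.03 to 5.30), or a subject-specific OR tied to a variance that cannot be estimated. The significance test is not the problem, since p is about 0.04 throughout.

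The sizes rest on assumed rates, 50 per arm and a single site. The flat likelihood in the two-arm case does not depend on those rates; it follows from one informative diagnosis per person. The plan should be corrected before analysis, but the fault is in the specification and does not invalidate the comparison.

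**What to change.** In section 10.4.2:

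- Replace PROC Mixed with GLS and REML by logistic regression on one record per participant (PROC LOGISTIC, or GLIMMIX with a logit link).
- Drop the subject random effect.
- Keep fixed centre terms for the pooled NYU, UCLA and FRI data.
- State how the site-by-treatment terms are averaged into the single primary contrast, for example by equal weights per site or by site size. With those interactions in a logit model, no single coefficient is the overall effect until the weights are given.
- Report the odds ratio, plus a standardised risk difference with its 95% CI, because the section words the contrast as a comparison of probabilities.

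The cost is SAP wording and modest programming, with no new data. The standardised risk difference needs a delta-method or bootstrap interval.
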